9. ADDITIONAL SPECIFICATIONS TO THE PROTOCOL

9.1 Standard Procedures

Within the framework of the idv system, the following standard ensemble of classic and
robust summarizing statistics will be provided for data description: mean, standard
deviation, standard error of the mean, minimum, lower quartile, median, upper quartile,
maximum, valid number. In addition, measures for skewness and kurtosis will be
provided for suitable efficacy variables. Where appropriate, the result presentation will
include changes from baseline.

• For categorical data, frequency counts will be provided with their associated percentages. Semi-quantitative and quantitative efficacy data will be additionally visualized by boxplot diagrams. All standardized effect sizes (Mann-Whitney) will be visualized with their corresponding 95%-confidence intervals. All standard statistical tables are generated with the standard table layout of the validated statistical package TESTIMATE V6.5.14 (IDV Gauting). Associated meta-data and variable labels are finalized before unblinding. All standard scientific figures are generated with the standard figure layout of the validated scientific package SCIENCEGRAPH V4.9.39 (IDV Gauting).

9.2 Demography and Baseline Characteristics

9.2.1 Operationalizations in Final Protocol

None.

9.2.2 Additional Operationalizations

- Besides standard descriptive analyses (see section 9.1), formal homogeneity analyses for demographic variables and baseline characteristics will be performed based on the full analysis set (FAS) and the per-protocol set (PP). Robust Mann-Whitney estimators and their 95% confidence intervals will used as standardized summary measures across the relevant demographic-anamnestic variables (demography, physical examination, vital signs, supportive therapy, time and grading of injury) as well as across the efficacy criteria at baseline (VAS pain on passive movement, VAS pain at rest, FAAM). This will be performed in order to check baseline comparability of the three randomized groups in a robust, nonparametric way (minimized assumptions, independent from data type).
- As benchmark for relevant baseline differences, a Mann-Whitney estimator of 0.36 and 0.64 respectively will be applied (referring to a standardized difference of 0.5 according to Cohen, which is regarded as a medium-sized difference).
- In the case of inhomogeneities, stratified analyses will be performed by means of the Peto-Wilcoxon test (2 sided; 95% confidence interval, CI) with adjustment within the framework of the Cochran-Mantel-Haenszel pooling procedure (CMH pooling, also known as van Elteren pooling). For this purpose, depending on the respective data type and distribution, nominal categories, medians or quartiles of the affected baseline criteria will be used for stratification.

9.3 Evaluations and Endpoints – First Line Analysis

9.3.1 Primary Efficacy Variable

9.3.1.1 Operationalizations in Final Protocol

Primary Efficacy Variable

Area under the curve (AUC)* for pain on passive movement in Visual Analog Scale (VAS) from baseline to Day 4

Confirmatory Analyses

1. AUC for pain on passive movement in VAS from baseline to Day 4 (test for superiority, Traumed[®] gel versus placebo), Full Analysis Set. The null and alternative hypotheses for the comparison of Traumed[®] gel versus placebo can be formulated as follows:

H₀: $\mu_T = \mu_P$ H_A: $\mu_T \neq \mu_P$

H₀: Null hypothesis; H_A: Alternative Hypothesis; T: Test Treatment; P: Placebo Treatment; μ: mean of population (AUC)

2. AUC for pain on passive movement in VAS from baseline to Day 4 (test for non-inferiority, Traumed® gel compared to diclofenac gel), Per-Protocol Analysis Set (PP). For the comparison of Traumed® gel versus diclofenac gel the null and alternative hypothesis can be formulated as follows:

H₀: $\mu_{T} - \mu_{R} > 25 \text{ [mm x days]}$

H_A: $\mu_{\text{T}} \cdot \mu_{\text{R}} \leq 25 \text{ [mm x days]}$

 H_0 : Null hypothesis; H_A : Alternative Hypothesis; T: Test Treatment; R: Reference Treatment; μ : mean of population (AUC)

Hypothesis no. 1 (superiority) is based on the FAS analysis set, while hypothesis no. 2 (non-inferiority) is based on the PP analysis set. This way, both hypotheses are based on the more conservative data set.

If the first *a priori* ordered test (superiority) shows statistical significance, the subsequent hypothesis (non-inferiority) can then be tested individually in a confirmatory manner according to the principle of *a priori* ordered hypotheses (for control of alpha using stepwise testing see [Maurer et al. 1995]).

^{*}All AUC calculations will be based on actual time of measurement.

The confirmatory analyses will be performed using an analysis of covariance (ANCOVA) with baseline pain VAS as covariate. Due to the expected small number of patients per center, an additional inclusion of center as covariate will not be performed (see also EMA Guideline on adjustment for baseline covariates, section 4.2.3., EMA/295050/2013).

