5.3. Selection of Study Population

Patients with acute unilateral Grade 1 or Grade 2 sprain of the lateral ankle will be enrolled. Grade 3 patients are not eligible as for them topical gel treatment is not appropriate.

Ankle sprains are classified by 3 grades of sprains:

- Grade 1 sprain (mild): Slight stretching and some damage to the fibres (fibrils) of the ligament. The joint is stable.
- Grade 2 sprain (moderate): Partial tearing of the ligament. If the ankle joint is examined and moved in certain ways, abnormal looseness (laxity) of the ankle joint occurs. Clinically partial instability.
- Grade 3 sprain (severe): Complete tear of the ligament. If the investigator pulls or pushes on the ankle joint in certain movements, gross instability occurs. The joint is instable.

Fracture of the ankle should be excluded by using e.g. the Ottawa Ankle Rules. In case of any doubt the exclusion of fracture by x-ray should be considered as per standard of care. After excluding fracture the investigator will evaluate the stability of the ankle joint using the anterior drawer test, the inversion stress manoeuvre and the external rotation test.

The mechanism of the injury and the clinical symptoms (edema, hematoma, location of pain at palpation) will be documented to support the grading.

The high pain and swelling might influence the outcome of the grading at Day 1, therefore a confirmatory check of the grading will be performed at Day 4. Patients who are classified having Grade 3 ankle sprain after randomisation and up to Day 4 will be withdrawn from the study and their data will not be part of the efficacy analysis but will be part of the safety analysis.

The investigators will be trained during the investigator meeting to ensure a consistent assessment and grading between investigators.

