5.3.1. Inclusion Criteria

Potential study patients must meet the following inclusion criteria:

1. Acute unilateral Grade 1 or Grade 2 sprain of the lateral ankle
2. ≥ 18 years of age
3. Legally competent male or female outpatient

-
4. Injury occurred within previous 24 hours before first treatment expected
 5. Signed Informed Consent
 6. After 5 minutes of rest, pain on passive movement by investigator measured by Visual Analog Scale (VAS) >50 mm
 7. Not pregnant (as proven by negative pregnancy test in case of woman of childbearing potential before first study drug administration) or breast-feeding. Females of childbearing potential must agree to maintain highly effective birth control throughout the study (see all details in section 9.6). Such methods include:
 - oral, intravaginal, transdermal combined (oestrogen and progestogen containing) hormonal contraception associated with inhibition of ovulation,
 - oral, injectable, implantable hormonal contraception associated with inhibition of ovulation, intrauterine device (IUD), intrauterine hormone-releasing system (IUS), bilateral tubal occlusion, vasectomized partner (if received medical assessment of the surgical success), sexual abstinence (only if defined as refraining from heterosexual intercourse during the entire period of trial participation).

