7.1. Schedule of Study Procedures

A schedule of study procedures and events is provided in Table 1.

Table 1 Schedule of Study Procedures

| | Initial Visit | Treatment Visits | | EoT Visit | Final Visit |
|--|--------------------|------------------|------------------|--------------------|---------------------|
| | Screening/Baseline | Visit 2 | Visit 3 | Visit 4 | Visit 5 |
| | Day 1 | Day 2 | Day 4 + 1 day | Day 7 +/- 1 day | Day 14 +/- 1 day |
| Informed Consent | X | | | | |
| Inclusion/Exclusion Criteria | X | | | | |
| Demographics | X | | | | |
| Pregnancy test (if applicable) | X | | | X | |
| Medical history | X | | | | |
| Time and grading of injury | X | | | | |
| Height/Weight (BMI) ¹ | X | | | | X ¹ |
| Physical examination including blood pressure and pulse | X | | | | X |
| Randomization | X | | | | |
| Dispense patient diary ² | X | | X | | |
| FAAM-ADL ³ | X | X | X | X | X |
| Pain at rest by Visual Analog Scale (VAS) ³ | X | X | X | X | X |
| Pain on passive movement by Visual Analog Scale (VAS) ³ | X | X | X | X | X |
| IMP tubes dispensed | X | | | | |
| Investigational treatment | X | X | X | X | |
| Application of soft support (elastic bandage) | X | X | X | X (as required) | X (as required) |
| Rescue medication dispensed | X | | X (if needed) | X (if needed) | |
| Diary reviewed | | X | X | X | X |
| Diary returned | | | X | | X |
| IMP tubes weighted | | | X | X | |
| Rescue medication reviewed | | X | X | X | X |
| IMP tubes returned and sealed | | | | X | |
| Rescue medication returned | | | | | X |
| Check use of other pain medication and record if any | X | X | X | X | X |
| Record previous/concomitant medication | X | X | X | X | X |
| Record Adverse Events ⁴ | X | X | X | X | X |
| Record use of arm crutches | X | X | X | X | X |
| Confirmatory check of grading | | | X | | |
| Application of semi-rigid brace for Grade 2 | | | | X | X |
| Question to patients which treatment they assume to have received | | | | | X |

¹ At Visit 5 (day 14) only the weight will be measured.

² The first patient diary will be collected on Day 4. The patient will receive second diary on the same day. ³

The time point of each visits/ measurements of patients shall be ideally the same at each visit (+/- 1 hour). ⁴

Including adverse events observed at the site of administration of the IMP (lateral ankle).

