11.4. Determination of Sample Size

Estimation of sample size is based on the primary efficacy variable. A two-sided test of equality of the study drug (Traumed[®] gel) and the comparator (placebo) at level 0.05 based on an expected raw scale treatment difference of AUC 25 [mm x days] and a common standard deviation of AUC 75 [mm x days] for the response variables (re-expressed for nonparametric evaluation in terms of the Mann-Whitney statistic as $MW = 0.6$ (see section 11.1.3), achieves a power of at least 90% for parametric first line analysis as well as for second line nonparametric analysis if the sample size is set to 291 patients for the Traumed[®] gel group and to 146 patients for the placebo group.

Due to an additional safety requirement that AEs with incidence level of 1% for Traumed[®] gel are found during the study with probability 95%, 299 patients for the Traumed[®] gel group are required. Assuming a drop-out rate from the Safety Analysis Set of about 4% an amount of 312 randomized patients in the Traumed[®] gel group is needed. With an allocation ratio of 2:1:1 (Traumed[®] gel : diclofenac gel : placebo) 156 patients are obtained in the diclofenac gel and placebo group each, that is, a total of 624 patients with acute unilateral Grade 1 or Grade 2 sprain of the lateral ankle.

In order to ensure the pre-defined power of the trial for the trial objectives including the confirmatory test for non-inferiority (Traumed[®] gel compared to diclofenac gel), which is based on the Per-Protocol Analysis Set (PP), a sample size enhancement is introduced for compensation of:

- cases for whom maintenance of blinding procedures may have been compromised and, thus, are representing a major protocol violation (exclusion from PP analysis).

For compensation, the final sample size will be enhanced to 202 patients for the diclofenac and Placebo group each, and to 404 patients for the Traumed[®] gel group resulting in a new total of 808 patients. *(revised per Amendment to protocol version 3.0)*

12. Study Report and Publication Policy

An integrated study report in accordance with the ICH Harmonized Tripartite Guideline (E3) (Structure and content of clinical study reports) will be developed.

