 - Covariates (within), an indication of the significance and relevance of the covariate for the criterion.
 - Test statistic for adjusted group differences, correct also for groups of unbalanced size.
 - Coefficient of determination R² for the amount of variation of the criterion, which is explained by the covariate and the differences between the groups.
 - Model parameter: the y-intercept and slope of the regression lines (slopes are now necessarily identical because of the reduction of the full model), adjusted mean values for a common value X₀ of the covariate.
- The analysis of covariance of the full model will be used for the confirmatory approach (the reduced regression model is provided as supportive information only)
- Descriptive Procedures: TESTIMATE V6.5.14; PROC BASIC STATISTICS / SCIENCEGRAPH V4.9.39
- Test Procedures: TESTIMATE V6.5.14; PROC ANALYSIS OF COVARIANCE

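### Day 1 sprain grade and hours since injury are recorded but left out of the confirmatory ANCOVA with no reason given, a likely modest loss of precision

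*SAP*

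**What the plan says.** **Model.** SAP 9.3.1.1 restates protocol 11.1.3: "The confirmatory analyses will be performed using an analysis of covariance (ANCOVA) with baseline pain VAS as covariate". SAP 9.3.1.2 fits a separate baseline-VAS regression line in each group and specifies that "The analysis of covariance of the full model will be used for the confirmatory approach". It also extends the ordered chain to four hypotheses by adding superiority and non-inferiority at Day 7. Center is the only other covariate discussed: "an additional inclusion of center as covariate will not be performed", because few patients per center are expected. Grade and time since injury are not mentioned.

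**Data.** The schedule in protocol 7.1 lists "Time and grading of injury" at Day 1. Protocol 7.2.1 requires the date and time of injury and of first treatment in the eCRF. Entry requires "Injury occurred within previous 24 hours before first treatment expected". Protocol 5.3 describes Grade 1 as "Slight stretching and some damage to the fibres (fibrils) of the ligament. The joint is stable", and Grade 2 as a partial tear with laxity.

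**Randomisation.** Protocol 6.1.2 describes permuted blocks and names no stratification by either variable.

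**Fallback.** SAP 9.2.2 includes time and grading of injury in a baseline homogeneity check with a Mann-Whitney benchmark of 0.36/0.64. "In the case of inhomogeneities, stratified analyses will be performed by means of the Peto-Wilcoxon test". The planned stratified sensitivity analyses in SAP 9.4.2 adjust for center and for a delayed Day 4 visit only.

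**The concern.** Pain in the first days after a sprain follows a recovery curve. Severity of the injury and position on that curve may predict the Day 4 AUC beyond a single baseline VAS score. If they do, leaving them out keeps explainable variation in the error term of every confirmatory comparison and widens the intervals for superiority and non-inferiority alike. No unconditional analysis, primary or sensitivity, uses either variable. Ordinary chance imbalance in grade would therefore never be adjusted for in the confirmatory estimate.

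**Working it through.** **1. The plan's own figure.** Inputs from protocol 11.4: difference 25 and SD 75 mm x days, two-sided 0.05, 90% power, 2:1.

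- n(placebo) = (1.960 + 1.282)² × 75² × (1 + 1/2) / 25² = 10.51 × 13.5 = 141.9, so 142, with 284 on Traumed. The plan has 146 and 291, within 3%.
- Power at 291:146 = Φ(25 / [75 √(1/291 + 1/146)] − 1.960) = Φ(25/7.606 − 1.960) = Φ(1.327) = 90.8%.

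The plan states no covariate reduction of the SD, so its power does not rest on these variables.

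**2. Patients after exclusion of issue cases.** 808 − 184 = 624, or 312:156:156 if enrolment is complete, the issue cases split 2:1:1, and nobody else is lost. Power at 312:156 = Φ(25/7.354 − 1.960) = 92.5%.

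**3. Gain from adjustment.** Let R² be the share of AUC variance that grade and time explain given baseline VAS. It is an assumption; the documents give no value. Residual SD = 75 √(1 − R²).

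| Assumed R² | Residual SD | Placebo n for 90% | Power 291:146 | Power 312:156 | 95% CI half-width, 312:156 |
|---|---|---|---|---|---|
| 0 | 75.00 | 142 | 90.8% | 92.5% | 14.41 |
| 0.02 | 74.25 | 140 | 91.3% | 93.0% | 14.27 |
| 0.05 | 73.10 | 135 | 92.1% | 93.7% | 14.05 |
| 0.10 | 71.15 | 128 | 93.4% | 94.8% | 13.67 |

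Hypothesis 2 has the same arithmetic (margin 25, true difference 0, one-sided 0.025). No SD is given for the Day 7 AUC, so hypotheses 3 and 4 cannot be sized.

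**4. How large R² might be.**

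- *Grade.* R² = p(1 − p)D²/75², where p is the Grade 2 share and D the baseline-adjusted AUC difference between grades, both assumed. For p from 0.3 to 0.5, D = 12.5 gives 0.6–0.7%, D = 25 gives 2.3–2.8%, and D = 50 gives 9–11%.
- *Time.* The earlier ankle-sprain trial summarised in protocol section 3 had baseline medians of 52.6–55.7 mm and day 7 medians of 16.0–21.6 mm. That is a fall of (52.6 − 21.6)/7 = 4.4 to (55.7 − 16.0)/6 = 6.6 mm per day. With entry times assumed uniform over 24 hours (SD 1/√12 day) and a 3-day AUC, the SD due to time is 3 × 4.4/√12 = 3.8 to 3 × 6.6/√12 = 5.7 mm x days. R² is then 0.3–0.6%, before baseline VAS absorbs any of it. A steeper assumed 15 mm per day gives 3.0%.

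**5. The trigger.** For a two-level factor, Mann-Whitney = 0.5 + (p1 − p2)/2, so 0.64 needs p1 − p2 = 0.28. At 312:156 the standard error of the difference is √[p(1 − p)(1/312 + 1/156)] = 0.039 for p = 0.2 and 0.049 for p = 0.5. The trigger therefore lies 7.1 to 5.7 standard errors from balance.

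**6. Chance imbalance below the trigger.** With p = 0.5, a two-standard-error imbalance is 2 × 0.049 = 9.8 points. With D of 25 to 50 it moves the estimate by about 2.5 to 4.9 mm x days, 10 to 20% of the margin of 25. This is the same imprecision as in step 3 seen in one sample, not an addition to it.

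**The case against.** The strongest reply is that nothing is broken. Under randomisation the VAS-adjusted comparison is valid, and the sample size reproduces without these covariates. Chance imbalance is already covered by the test's error rate and interval. All of this stands. A reader might infer bias, invalidity or a power shortfall from the omission; the documents support none of these. Nor does the conditional check in SAP 9.2.2 threaten error control, since it leads only to a supplementary rank analysis. The point about it is only that it does not fill the gap.

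A second reply is that prognostic value is assumed. This also stands. Protocol 5.3 warns that pain and swelling may influence the Day 1 grading, so grade may be noisy and partly duplicate baseline VAS. Because time adds so little, grade must carry most of any R². Reaching 0.05 by grade alone needs D = √(0.05 × 75²/[p(1 − p)]) = 34 to 37 mm x days for p of 0.5 to 0.3, above the treatment difference of 25 that the plan calls clinically important. It is therefore too strong to say that avoidable variation is known to remain. Baseline pain at rest and FAAM-ADL are also recorded, and no document shows that grade or time predicts better than these.

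A third reply is that the model is protocol text and that changing it after hard lock is more than a wording edit. That is fair as to documentation, but it does not block the change. SAP section 3 places signature before unblinding, and the same blind review already added two confirmatory hypotheses.

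**Conclusion.** The omission is confirmed: two baseline descriptors of the injury, known by the first dose, are absent from the confirmatory model for all four hypotheses. No reason is given, and the only fallback is practically unreachable for grade and never alters the confirmatory estimate. The consequence is a likely modest loss of precision, mainly from grade. Over assumed R² from 0 to 0.10 the gain is 0 to 2.6 power points at 291:146 (90.8% to 93.4%) and 0 to 2.3 points at 312:156 (92.5% to 94.8%).

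These figures treat 75 as the SD remaining after baseline VAS. If it is the unadjusted SD, starting power is higher and the gain in points smaller. This is an inexpensive improvement to a valid analysis, not the correction of an error.

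**What to change.** Before unblinding, in SAP 9.3.1.2, add Day 1 grade (1 or 2) and hours from injury to first treatment as covariates in the ANCOVA for hypotheses 1 to 4. Give each a slope common to all groups, alongside the existing group-specific baseline-VAS slopes. The treatment contrast is then still read at the common mean baseline VAS. Use the Day 1 grade; the Day 4 re-grade is made after randomisation. Record this in SAP section 8 as a change to protocol 11.1.3, and keep the VAS-only ANCOVA as a supporting analysis.

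No new data are needed. The cost is two degrees of freedom, a documented late change to the protocol's model, and a check that the named ANCOVA procedure can fit it, since the SAP describes only one covariate. The gain may be small if Day 1 grade largely duplicates baseline pain.

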9.3.1.2 Additional Operationalizations

- Visit 4 (Day 7) will be introduced as additional primary endpoint in the chain of a priori ordered hypotheses, leading to the following final sequence of confirmatory analyses:
 - 1. AUC for pain on passive movement in VAS from baseline to Day 4 (test for superiority, Traumed® gel versus placebo)
 - 2. AUC for pain on passive movement in VAS from baseline to Day 4 (test for non-inferiority, Traumed® gel compared to diclofenac gel)
 - 3. AUC for pain on passive movement in VAS from baseline to Day 7 (test for superiority, Traumed® gel versus placebo)
 - 4. AUC for pain on passive movement in VAS from baseline to Day 7 (test for non-inferiority, Traumed® gel compared to diclofenac gel)

If the preceding *a priori* ordered test shows statistical significance, the subsequent hypothesis can then be tested individually in a confirmatory manner according to the principle of *a priori* ordered hypotheses (for control of alpha using stepwise testing see [Maurer et al. 1995]).

Comment: The original endpoints at Day 4 remain unchanged (hypotheses no. 1 and no. 2), however Day 7 is introduced as additional primary endpoint in the chain of *a priori* ordered hypotheses (hypotheses no. 3 and no. 4). This addition is implemented as per BDRM decision in order to avoid lack of assay sensitivity at the early stage of the ankle joint injury (C1502_MTG_NOTES_BDRM_09MAR2021_20210324).

- Descriptive procedures will be performed according to section 9.1.
- For the analysis of covariance, in addition to the table with descriptive statistics and the
 analysis of variance of the covariate (test for homogeneity of the groups with respect to
 the covariate), the following results of the analysis of covariance will be generated:
 - Analysis of covariance of the full model (separate regression lines for each group) with the following information:
 - Test for parallelism and group difference at X₀ as an indication of group differences in case the regression lines are not parallel (for the hypothesis of parallelism a 10%-level will be applied).

- Model parameter: for each group, the point of intersection of the regression line, the slope and the adjusted mean value of X₀, the common mean value of the covariates for all groups.
- Analysis of covariance for the reduced regression model (a single regression line for all groups for the assumption that the regression lines are parallel), with the following information:
 - Covariates (within), an indication of the significance and relevance of the covariate for the criterion.
 - Test statistic for adjusted group differences, correct also for groups of unbalanced size.
 - Coefficient of determination R² for the amount of variation of the criterion, which is explained by the covariate and the differences between the groups.
 - Model parameter: the y-intercept and slope of the regression lines (slopes are now necessarily identical because of the reduction of the full model), adjusted mean values for a common value X₀ of the covariate.
- The analysis of covariance of the full model will be used for the confirmatory approach (the reduced regression model is provided as supportive information only)
- Descriptive Procedures: TESTIMATE V6.5.14; PROC BASIC STATISTICS / SCIENCEGRAPH V4.9.39
- Test Procedures: TESTIMATE V6.5.14; PROC ANALYSIS OF COVARIANCE

